#### **5.6.7 Prior and Concomitant medication**

Prior medications are defined as drugs taken and stopped prior to first dose of study medication.

Concomitant medication is defined as any medication, other than the Investigational Medicinal Product (IMP), which is given at least once between the day of first dose of randomized study medication and the last day of study visit (including those which were started pre-baseline and continued into the treatment period), including prescription and over-the-counter medicines, and any traditional or herbal remedies.

Paracetamol as an antipyretic, and metopimazine for repeated vomiting (or if not available, any other antiemetic which is not known to prolong QT and/or cause torsade de pointes) will be allowed. If paracetamol or equivalent drug is given as an antipyretic up to 72 hours prior first dose, it has to be reported as prior medication.

Metoclopramide is contraindicated from the period prior to first dose to Day 5 post-dose (120 hours).

Beta-lactam antibiotics can be given in case of a bacterial infection appearing after enrolment. All other antibiotics, new-quinolones included, should be avoided where possible.

The investigator must instruct the patient to notify the study site about any new medications he/she takes after the patient was enrolled into the study. All medications, procedures and significant non-drug therapies (including physical therapy and blood transfusions) administered after the patient was enrolled into the study must be recorded in the concomitant medications eCRF.

Each concomitant drug must be individually assessed against all exclusion criteria/prohibited medication. If in doubt the investigator should contact the Novartis medical monitor before randomizing a patient or allowing a new medication to be started.

## 5.6.8 Prohibited medication

### 5.6.8.1 Drug with potential impact on efficacy & safety

**Drugs with antimalarial effect:** Drugs/supplements which are known to have antimalarial effects are NOT allowed within minimum of their five (5) plasma half-lives (or minimum of 4 weeks if half-life is unknown) prior to enrollment and during the entire study period. They may be used in the course of managing a patient which has developed early or late treatment failure (ETF or LTF) or failed to respond to standard-of-care.

Lumefantrine-based treatments should not be used even in the case of treatment failure, at least up to Day 28 post last dose.

**Drug with QTc Potential:** Drugs/supplements which have potential to increase QTc interval such as but not limited to antiarrhythmic drugs, neuroleptics and antidepressant agents, metoclopramide, macrolides and fluoroquinolones antibiotics, imidazole and triazole antifungal agents, certain non-sedating antihistamines (terfenadine, astemizole), and cisapride, should be avoided during the study and within minimum of their five (5) plasma half-lives of last dose (or minimum of 14 days if unknown ) prior to dosing. Furthermore, drugs that slow the heart rate (HR), like digitalis and beta blockers should be avoided.

**Drugs with potential liver safety concerns:** Drugs which are known to have potential hepatotoxicity should not be used during study and within minimum of their five (5) plasma half-lives of last dose (or minimum of 14 days if half-life is unknown) prior to dosing. This includes NSAIDs (also over-the-counter medicines) and herbal medicines. Paracetamol < 4g/day (or equivalent pediatric dosage; 10 to 15 mg/kg orally every 4 to 6 hours) may be used however, exact doses and time should be recorded appropriately.

### 5.6.8.2 Drug with potential for pharmacokinetic interaction:

[figure not shown]
**Drugs/supplements impacting KAF156 and lumefantrine exposure:** drugs or supplements which are known CYP3A inhibitors (e.g., erythromycin, ketoconazole, itraconazole, cimetidine) or CYP3A inducers (e.g. rifampin, phenobarbital) etc. should not be used during study and within 14 days prior to dosing.

**Drugs/Supplements which can be impacted by KAF156 and lumefantrine:** KAF156 and lumefantrine both have strong potential for inhibition of CYP2D6 enzyme and KAF156 also has strong potential for inhibition of CYP3A enzyme. It has relatively lower inhibition potential for CYP2C8, CYP2C9 and CYP2B6 enzyme and OATP1B1 transporter. The following table (Table 5-5) lists drugs which have either been shown to increase 5-fold or higher when co-administered with a known CYP inhibitor or whose exposure-response relationship indicated that small increases in their exposure levels by the concomitant use of CYP inhibitors may lead to serious safety concerns. These drugs should not be used within 14 days or at least within their 5 half-lives of last dose prior to dosing. These drugs should also not be used during the study period or at least up to Day 29 post last dose even in the course of treating an adverse event. If this cannot be avoided, extreme caution is advised and dosing and monitoring should be adjusted to account for the possible CYP enzyme inhibition. Drugs outside of this list may be used to treat adverse events unless they are recognized as falling into either of the two categories listed in the table.

**Table 5-5 Prohibited medications**

CYP Enzymes/transporter	Sensitive substratesa	Substrates with narrow therapeutic rangeb
CYP2D6	Atomoxetine, desipramine, dextromethorphan, metoprolol, nebivolol, perphenazine, tolterodine, venlafaxine	Thioridazine, neuroleptics, flecainide, metoprolol, and tricyclic antidepressants such as imipramine, amitriptyline, clomipramine
CYP3A	Alfentanil, aprepitant, budesonide, buspirone, conivaptan, darifenacin, darunavir, dasatinib, dronedarone, eletriptan, eplerenone, everolimus, felodipine, indinavir, fluticasone, lopinavir, lovastatin, lurasidone, maraviroc, midazolam, nisoldipine, quetiapine, saquinavir, sildenafil, simvastatin, sirolimus, tolvaptan, tipranavir, triazolam, vardenafil	Alfentanil, astemizole, cisapride, cyclosporine, dihydroergotamine, ergotamine, fentanyl, pimozone, quinidine, sirolimus, tacrolimus, terfenadine
CYP2B6c	Bupropion, efavirenz	
CYP2C8	Repaglinide d	Paclitaxel
CYP2C9	Celecoxib	Warfarin, phenytoin
OATP1B1	Bosentan, pravastatin	

a Sensitive CYP substrates refers to drugs whose plasma AUC values have been shown to increase 5-fold or higher when co-administered with a known CYP inhibitor.

b CYP substrates with narrow therapeutic range refers to drugs whose exposure-response relationship indicates that small increases in their exposure levels by the concomitant use of CYP inhibitors may lead to serious safety concerns (e.g., Torsades de Pointes).

c The AUC of these substrates were not increased by 5-fold or more with a CYP2B6 inhibitor, but they represent the most sensitive substrates studied with available inhibitors evaluated to date.

d Repaglinide is also a substrate for OATP1B1, and KAF156 potentially inhibits therapeutic OATP1B1 as well.

Except for medication which may be required to treat adverse events, no new medication other than study drugs will be allowed from the first dosing until up to completion of Day 7 evaluations.

Should a patient have an *incidental and limited* need for a medication to be taken within the restricted pre-dose timeframe (e.g., antibiotic prophylaxis prior to dental surgery, etc.), the sponsor should be advised, as administration of any concomitant medication *may* require the patient to be withdrawn from the study. Decisions regarding withdrawal from study participation will be discussed with the sponsor on a case-by-case basis. Administration of paracetamol < 4 g/day (or equivalent pediatric dosage; 10 to 15 mg/kg orally every 4 to 6 hours) as an antipyretic is acceptable. If within 36 hours of study drug administration, infections other than malaria require the administration of drugs with antimalarial activity (such as co-trimoxazole, tetracycline, doxycycline, etc.), with the exception of the use of topical antibiotics, the patient will be followed up until the end of the study.

## 5.7 Study completion and discontinuation

### 5.7.1 Study completion and post-study treatment

Each patient will be required to complete the study in its entirety and thereafter no further study treatment will be made available to them.

A patient will be considered to have completed the study when the patient has completed the last visit planned in the protocol, and any repeat assessments associated with this visit have been documented and followed-up appropriately by the investigator.

Patients who discontinue study drug and are put on rescue medication will be followed for the entire study duration (i.e., until Day 43).

The investigator and/or referring physician must provide follow-up medical care for all patients who are prematurely withdrawn from the study, or must refer them for appropriate ongoing care. This care may include:

- Treatment of their malaria and complications
- Treatment of secondary infections
- Treatment of associated diseases

An independent Data Monitoring Committee (DMC) will review patient safety at several time points (see [Section 8.4](#)) and may recommend stopping a cohort or the study early for safety reasons.

### 5.7.2 Discontinuation of study treatment

Patients will be treated under hospital supervision during the treatment period. Discontinuation of study treatment for a patient occurs when study drug is stopped earlier than the protocol

planned duration, and discontinuation can be initiated by either the patient or the investigator. For patients assigned to 1-day and 2-day cohorts, they will not be considered as treatment discontinuation if those discontinuation events occur after they have completed the treatment as assigned.

The investigator must discontinue study treatment for a given patient if, on balance, he/she believes that continuation would negatively impact the patient's risk of trial participation.

Study treatment must be discontinued under the following circumstances:

[figure not shown]
- Patient request
- Pregnancy (see [Section 6.5.6](#) and [Section 7.7](#))
- Use of prohibited treatment as per recommendations in [Table 5-5](#)
- Any situation in which study participation might result in a safety risk to the patient and/or any adverse events that in the judgment of the investigator, taking into account the patient's overall status, prevent the patient from continuing participation in the study
- Unsatisfactory therapeutic effect (see [Section 6.5.8](#))
- Emergence of the following adverse events: severe nausea/vomiting, severe pruritus, increases in QTcF to > 500 ms (based on repeat ECGs), development of ventricular arrhythmia or clinically significant (symptomatic) bradycardia (see [Appendix 3](#))
- Any laboratory abnormalities that in the judgment of the investigator, taking into consideration the patient's overall status, prevent the patient from continuing participation in the study (e.g., increase in liver enzymes > 3 times the upper limit of normal (see [Appendix 2](#)))
- Deviation from the planned dose regimen for the study drug (e.g., vomiting of the replacement dose within 2 hours of intake)

Patients who discontinue study drug for any of the above reasons may be given rescue medication at the discretion of the investigator and will be followed for the whole study duration until Day 43.

If discontinuation of study treatment occurs, the patient should NOT be considered withdrawn from the study and should undergo the scheduled study visits. The investigator must determine the primary reason for the patient's premature discontinuation of study treatment and record this information on the Treatment Completion eCRF. If the patient completes all the scheduled visits in the treatment Epoch, the patient is considered to have completed the treatment Epoch. If a patient does not complete the scheduled visits in the treatment Epoch, premature treatment discontinuation visit assessments detailed in the table of assessment should be completed and recorded in the eCRF.

If the patient cannot or is unwilling to attend any visit(s), the site staff should maintain regular telephone contact with the patient, or with a person pre-designated by the patient, to collect key safety data. This telephone contact should preferably be done according to the study visits schedule.

The investigator must also contact the IRT to register the patient's discontinuation from study treatment (this patient will not be replaced).

### 5.7.3 Premature Study Withdrawal

Patients are considered to be withdrawn prematurely from the study if they do not complete the follow-up visits until Day 43.

A patient may voluntarily discontinue participation in this study at any time. The investigator may also, at their discretion, discontinue the patient from participating in this study at any time. Patients may be prematurely discontinued from the study for any of the following reasons:

- Adverse event
- Protocol deviation
- Study closed/terminated
- Loss to follow-up
- Consent withdrawal
- Study or investigator non-compliance
- At the request of the patient, investigator, or sponsor
- Pregnancy

Patients are not obligated to state the reason for withdrawal from this study. However, the reasons for withdrawal, or failure to provide a reason, must be documented by the investigator on the Completion/Withdrawal section of the eCRF.

If a patient is withdrawn from the study for any reason, the investigator must make every effort to perform the study evaluations for Withdrawal visit as specified in the [Table 6-1](#). Withdrawn patients will not be replaced.

### 5.7.4 Withdrawal of informed consent

Patients may voluntarily withdraw consent to participate in the study for any reason at any time. Withdrawal of consent (WoC) from the study is defined as when a patient:

- Does not want to participate in the study anymore

and/or

- Does not want any further visits or assessments

and/or

- Does not want any further study related contacts

[figure not shown]
and/or

- Does not allow analysis of already obtained biologic material

In this situation, the investigator must make every effort (e.g. telephone, e-mail, letter) to determine the primary reason for the patient's decision to withdraw his/her consent and record this information.

Study treatment must be discontinued and no further assessments conducted, and the data that would have been collected at subsequent visits will be considered missing.

Further attempts to contact the patient are not allowed unless safety findings require communicating or follow-up.

All efforts should be made to complete the assessments prior to study withdrawal. A final evaluation at the time of the patient's study withdrawal should be made as detailed in the assessment table below.

#### **5.7.5 Loss to follow-up**

For subjects whose status is unclear because they fail to appear for study visits without stating an intention to discontinue or withdraw, the investigator must show "due diligence" by documenting in the source documents steps taken to contact the subject, e.g. dates of telephone calls, registered letters, etc. A patient cannot be considered as lost to follow-up until the time point of his/her scheduled end of study visit has passed.

#### **5.7.6 Early study termination by the sponsor**

The study can be terminated by Novartis at any time for any reason. This may include reasons related to the benefit risk assessment of participating in the study, practical reasons, or for regulatory or medical reasons (including slow enrolment). Should this be necessary, the patient must be seen as soon as possible and treated as a prematurely withdrawn patient. The investigator may be informed of additional procedures to be followed in order to ensure that adequate consideration is given to the protection of the patient's interests. The investigator will be responsible for informing the Institutional Review Board/Independent Ethics Committee (IRBs/IECs) of the early termination of the trial.

## **6 Visit schedule and assessments**

Patients must be seen for all visits on the designated day, or as close to it as possible. Missed or rescheduled visits should not lead to automatic discontinuation. Patients who prematurely discontinue the study for any reason should be scheduled for a visit as soon as possible, at which time all of the assessments listed for the final visit in the Epoch will be performed. At this final visit, all dispensed investigational product should be reconciled and the adverse event and concomitant medications recorded on the eCRF. An overview of the specific CRF pages are listed on [Table 6-5](#) (for database development purposes). The PK Run-in Part will follow the same visit schedule as for Cohorts 1 and 2 which have QD dosing for 1 day.

UNS = Unscheduled visit

EOT = End of Treatment

PSW = Premature Study Withdrawal

X = assessment to be recorded on clinical database

S = assessment to be recorded on source documentation only

 Patients will be admitted to the hospital on Day 1 and will remain in the hospital under close supervision until they are discharged by the investigator or designee on Day 4.

 Visit structure given for internal programming purpose only.

 Fever monitoring will be done every 6 hours until resolution of fever, defined as being afebrile for 24 hours.

 Comparator only (Coartem®). Coartem® will be given at 0, 8, 24, 36, 48 and 60 hours. For all drug administrations actual time should be recorded.

 Not applicable to 1-day treatment regimen.

 Not applicable to 1 and 2-day treatment regimens.

 A complete physical examination will be performed by the investigational staff at screening and include the examination of general appearance, skin, neck (including thyroid), eyes, ears, nose, throat, lungs, heart, abdomen including splenomegaly, back, lymph nodes, extremities, vascular and neurological. Malaria signs and symptoms, body height and body weight will also be recorded at screening as part of the complete physical examination.

An abbreviated physical examination will be performed at all other visits starting from Day 1. An abbreviated physical exam will include the examination of general appearance and malaria signs and symptoms. Body weight will also be measured at End of Study Visit (Day 43 or earlier in case of premature patient discontinuation).

 Laboratory tests should also be taken at any time of withdrawal/discontinuation. [REDACTED]

 The patient's menstrual and contraceptive history will be taken and a urine  $\beta$ -hCG pregnancy test will be performed at screening to exclude pregnancy and at end of study. Results must confirm negative before dosing.

 Pre-screening parasite count should be used as baseline count. In case parasite count has been done > 6 hours before Study Visit 99 then it should be repeated at Study Visit 99 and the outcome of the repeated test should be considered as baseline parasite count

 PCR will be used for genotyping to establish malaria recrudescence/reinfection. PCR blood samples will be used for reviewing resistance markers. At screening, blood sample will be collected in all patients fulfilling eligibility criteria for inclusion in the study. A second blood sample collected as per Table above will be analyzed only in patients showing treatment failure before standard-of-care is administered.

[REDACTED]

 Meals within 3 hours prior to dosing and within 4 hours post-dosing to be documented.

 IRT has to be notified at Study Visit 1, at each study drug dispensing and at the completion or discontinuation of study treatment, upon completion of study or premature withdrawal from study participation. Also, if a patient vomits study drugs and needs to take a replacement medication, the site staff need to notify IRT.

[REDACTED]

 Screen Epoch has 2 parts: a Pre-Screening Part (Study Visit 1) to successfully identify the correct patients to be screened for this clinical study, and a Screening Part (Study Visit 99) in which further assessments will take place.

**Table 6-2 12-Lead ECG assessments (triplicate) for all patients (PK Run-in Part, Part A and Part B)**

Epoch	Screen		Treatment 														Follow-up						UNS		
	1	99	101						102				199				201	202	203	204	205	299			
Visit Numbers 													EOT Epoch / premature discontinuation									End of Follow up / PSW			
Study Day			1						2				3				4	5	8	15	29	43			
Window			±0 day						±0 day				±0 day				±0 day	+1 day	±1 day	±2 day	±4 days	±4 days			
Time (post-dose) in hours	-24 to <0		0	1	3	6	8	12	18	24	27	30	36	48	51	54	60	68	72	96	168	336	672	1008	
KAF-LUM SDF 1D cohort		x			x	x			x 	x		x 									x			x	
KAF-LUM SDF 2D cohort		x				x 				x	x	x		x							x			x	
KAF-LUM SDF 3D cohort		x				x 				x				x	x	x			x		x			x	
Coartem cohort		x				x 											x				x			x	

**Note: ECG's should be taken in triplicate within 5 minutes after resting for at least 10 minutes in the supine position to ensure a stable heart rate according to the ECG investigator manual. Also, ECG's should be taken before any other procedure taken at the same nominal time point is performed. For Scheduled time ≤ 2 h ± 10 min; 2 to < 24 h ± 30 min; ≥ 24 to 72 h ± 2 h; > 72 h ± 24 h.**

UNS = Unscheduled visit

EOT = End of Treatment

[figure not shown]
PSW = Premature Study Withdrawal

X = assessment to be recorded on clinical data base

 Patients will be admitted to the hospital on Day 1 and will remain in the hospital under close supervision until they are discharged by the investigator or designee on Day 4.

 Visit structure given for internal programming purpose only.

 ECG assessment at this time point to be done for patients in Part A only, ECG assessments will be repeated in case of abnormalities.

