**Table 6-3 PK sampling schedule for patients involved in RICH PK sampling (PK Run-in Part and Part A)**

Epoch	Screen		Treatment 														Follow-up					UNS															
Visit Numbers 	1	99	101							102							199														299 End of Follow up / PSW						
			EOT Epoch / premature discontinuation														201	202	203	204	205																
Study Day			1							2							3														4	5	8	15	29	43	
Window			±0 day							±0 day							±0 day														±0 day	+1 day	±1 day	±2 day	±4 days	±4 days	
Time (post-dose) in hours	-24 to <0		0	1	3	6	8	12	18	24	27	30	36	48	51	54	60	68	72	96	168	336	672	1008													
KAF-LUM SDF 1D cohort			X 	x	x	x		x	x	x		x		x					x	x																	
KAF-LUM SDF 2D cohort			X 	x	x	x		x		x	x	x	x	x				x	x	x																	
KAF-LUM SDF 3D cohort			X 	x	x	x		x		x				x	x	x		x	x	x	x																

**Notes:** A) Each PK sample will be 1mL blood. Further details on sample collection, numbering, processing and shipment can be found in the Site Operations Manual. B) Missed PK sampling time should be taken as soon as possible and actual time should be recorded. For Scheduled time ≤ 2 h ± 10 min; 2 to < 24 h ± 30 min; ≥ 24 to 72 h ± 2 h; > 72 h ± 24 h.

UNS = Unscheduled visit

EOT = End of Treatment

[figure not shown]
PSW = Premature Study Withdrawal

X = assessment to be recorded on clinical data base

 Patients will be admitted to the hospital on Day 1 and will remain in the hospital under close supervision until they are discharged by the investigator or designee on Day 4.

 Visit structure given for internal programming purpose only.

 PK sampling at Visit 101 should be done in a range of 15 min to 1 min prior to dosing.

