**Table 6-5 Overview of specific CRF pages**

Epoch	Screen		Treatment 														Follow-up					UNS						
Visit Numbers 	1	99	101							102							199		201	202	203	204	205	299				
			EOT Epoch / premature discontinuation														End of Follow up / PSW											
Study Day			1							2							3					4	5	8	15	29	43	
Window			±0 day							±0 day							±0 day					±0 day	+1 day	±1 day	±2 day	±4 days	±4 days	
Time (post-dose) in hours	-24 to <0		0	1	3	6	8	12	18	24	27	30	36	48	51	54	60	68	72	96	168	336	672	1008				
Screening Epoch disposition page 	x	x																										
Treatment completion 			x				x 			x 			x 	x 			x 											
Treatment Epoch disposition page 																		x										
Follow-up Epoch disposition page 																									x			

UNS = Unscheduled visit

EOT = End of Treatment

PSW = Premature Study Withdrawal

X = assessment to be recorded on clinical data base

 Patients will be admitted to the hospital on Day 1 and will remain in the hospital under close supervision until they are discharged by the investigator or designee on Day 4.

 Visit structure given for internal programming purpose only.

 To be completed at the last study drug administration.

 Comparator only (Coartem®).

[figure not shown]
 Not applicable to 1-day treatment regimen.

 Not applicable to 1 and 2-day treatment regimens.

 To be completed at End of Treatment (EOT) Epoch (end of Day 3 or at the time of treatment Epoch discontinuation).

 To be completed at end of follow-up Epoch (Day 43 or at the time of follow-up Epoch discontinuation).

 The Screen Epoch disposition page is completed at Visit 1 if a patient is a screen failure at Visit 1 and at Visit 99 otherwise.

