2.1.1 General definitions

Study treatment: KAF156, Lumefantrine solid dispersion formulation (LUM-SDF), and Coartem[®]. KAF156 and LUM-SDF are part of investigation treatments whereas Coartem[®] will be served as control. They are referred to as study treatments in the document.

Treatment group name, instead of cohort number, will be used in statistical analyses and outputs. The following abbreviated treatment groups will be used as the headers in the CSR outputs:

- KAF200 mg/LUM960 mg-1D (for PK run-in part) or KAF200 mg/LUM960 mg-1D in case the description is too long
- KAF400 mg/LUM960 mg-1D
- KAF800 mg/LUM960 mg-1D
- KAF400 mg/LUM960 mg-2D
- KAF200 mg/LUM480 mg-3D
- KAF400 mg/LUM480 mg-3D
- KAF400 mg/LUM960 mg-3D
- Coartem

Baseline: The last measurement made prior to administration of the first dose of study treatment. Note this may include measurements taken on the day of randomization (e.g. lab, ECG, vitals). If a patient did not receive any dose of study treatment then the date at randomization date will be used as the date of first dose of study treatment.

Study day: Study day will be calculated with respect to the first dose of study treatment. The first day of administration of study treatment (first dose) is defined as Day 1. Day -1 will be the day before Day 1. Day 0 does not exist. Due to the multiple assessments collected more than once for a day in the treatment phase for some variables, the study day calculation is based on the treatment start date and time.

For the assessments that are performed more than once for a day:

On or after Day 1 up to Day 3, study day = Integer (datetime of assessment – datetime of first dose of study treatment)/(60*60*24) + 1.

For assessments collected after Day 3, study day = date of assessment – date of first dose of study treatment + 1.

For assessments that are performed once for a day: study day = date of assessment – date of first dose of study treatment + 1.

For assessments collected prior to Day 1, study day = date of assessment - date of first dose of study treatment.

Tail of KM plots: Since the tail of KM plots after the day of last planned assessment is not reliable due to small numbers of patients at risk, the time to event will be reset to planned last day regardless of censoring.

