2.8.3 Other safety data

2.8.3.1 ECG and cardiac imaging data

The following quantitative variables will be summarized for averaged triplicate ECG: heart rate, RR interval, PR interval, QRS interval, QT interval, QTcB (QT interval corrected for heart rate according to Bazett) and QTcF (QT interval corrected for heart rate according to Fredericia).

Descriptive summary statistics for the change from baseline for each post-baseline visit will be performed by ECG parameters and treatment group.

Patients with notably high QT, HR and fever ($\geq 37.5^\circ\text{C}$ for *axillary* or $\geq 38.3^\circ\text{C}$ for other routes) will be provided.

To assess the temporal correlations mean change of QTcF over time, mean change of ECG HR over time, mean change of temperature over time, and PK concentration of KAF156 and lumefantrine over time will be plotted with all panels aligned on the x-axis (Time after dosing).

QTc will be summarized categorically by computing the number and percentage of patients at each time point and at the maximum post baseline value with following:

- QT, QTcF, or QTcB
 - > 450 and ≤ 480 ms
 - > 480 and ≤ 500 ms
 - > 500 ms
 - Increase from Baseline of ≥ 30 ms to < 60 ms
 - Increase from Baseline of ≥ 60 ms
- HR for age ≥ 18 years
 - Increase from baseline $>25\%$ and to a value > 100 bpm
 - Decrease from baseline $>25\%$ and to a value < 50 bpm
- HR for age < 18 years
 - $>$ upper limit of normal (ULN) defined in Table 2-3
 - $<$ lower limit of normal (LLN) defined in Table 2-3
- PR

- Increase from baseline >25% and to a value > 200 ms
- New value of > 200 ms
- QRS
 - Increase from baseline >25% and to a value > 120 ms
 - > 120 ms

Table 2-3 Normal heart rates (resting) by age

Age (years)	Normal range bpm
1 - ≤ 3	70 - 110
3 - ≤ 6	65 -110
6 - ≤12	60 -95
>12	55 -85

Source: Nelson Textbook of Pediatrics, 18th Edition

A line plot by patient (Spaghetti plot) will be provided by visit and treatment group.

In addition, shift tables comparing baseline ECG results (normal, abnormal, not available, total) with the post-baseline results will be provided by visit and at the worst post-baseline result (normal, abnormal, not available, total).

A listing of all newly occurring or worsening abnormalities as compared with baseline will be provided, as well as a by-patient listing of all quantitative ECG parameters.

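### The ±2 h tolerance makes the Day 2 and Day 3 ECG and PK times overlap, and SAP Table 5-6 files some compliant readings under the next timepoint

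*Protocol*

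**What the plan says.** **Tolerances.** The notes to Protocol Table 6-2 (ECG), Table 6-3 (rich PK) and Table 6-4 (sparse PK) carry the same rule: "2 to < 24 h ± 30 min; ≥ 24 to 72 h ± 2 h".

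**Schedule.** In Table 6-2 the row "KAF-LUM SDF 2D cohort" has ECGs at 24, 27 and 30 h, and the row "KAF-LUM SDF 3D cohort" at 48, 51 and 54 h. The PK tables use the same times. Table 6-5 places treatment completion at 24 h and 48 h, the latter marked "Not applicable to 1 and 2-day treatment regimens", so the repeat doses fall nominally at those hours. The visit window for those days is ±0 day. The schedule tables state no hour limit for the repeat dose.

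**Order of procedures.** Table 6-2 adds that "ECG's should be taken before any other procedure taken at the same nominal time point is performed", which makes the 24 h and 48 h ECGs nominally pre-dose. For PK, pre-dose timing is explicit only at the start: "PK sampling at Visit 101 should be done in a range of 15 min to 1 min prior to dosing".

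**Analysis windows.** SAP 5.1.4 re-aligns every visit into a window. The SAP's clock runs from the first dose: study day for repeated assessments uses "datetime of assessment – datetime of first dose of study treatment", and Table 5-6 sets baseline at 0 h. For both ECG and PK, Table 5-6 ends the 24, 27, 48 and 51 h windows at 25, 28, 49 and 52 h. If two readings share a window, Table 5-7 keeps the one nearest the target for by-visit summaries (the earlier if tied) and the most extreme for notable abnormalities.

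**The concern.** Points 3 h apart cannot each carry ±2 h without sharing permitted time, and the SAP then reassigns readings by elapsed time rather than by the timepoint they were taken for. A site can follow the protocol exactly and still have its 24 h reading analysed as 27 h.

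These readings surround the last dose in the 2-day and 3-day arms. As Table 6-2 reads, those arms have no 3 h ECG after dose 1. The 27 h and 51 h ECGs are therefore their only scheduled 3 h post-dose ECGs. SAP 2.8.3.1 tabulates QTc categories at each timepoint and summarises change from baseline by visit. It also plans aligned plots, introduced with "To assess the temporal correlations mean change of QTcF over time". Protocol 3.1 lists QTc and drug exposure among the endpoints of the interim assessment that informs Part B. At stake is whether the 24, 27 and 30 h cells, and the 48, 51 and 54 h cells, contain what their labels suggest.

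**Working it through.** **1. Reproduce the SAP cut-points.** SAP 5.1.4 sets the upper limit as the target plus the integer part of half the gap to the next target. Applied to the hour targets of Table 5-6:
- 24 + int(3/2) = 25; 27 + int(3/2) = 28
- 48 + int(3/2) = 49; 51 + int(3/2) = 52

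All four match Table 5-6. Truncating 1.5 to 1 leaves only 1 h after each target, so readings cross forward and (apart from exact boundary times) not back.

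**2. Permitted intervals against SAP windows.**

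| Nominal time | Permitted (±2 h) | SAP upper cut | Compliant but moved to next timepoint |
|---|---|---|---|
| 24 h | 22–26 | 25 | >25 to 26 |
| 27 h | 25–29 | 28 | >28 to 29 |
| 30 h | 28–32 | 39 ECG, 33 PK | none |
| 48 h | 46–50 | 49 | >49 to 50 |
| 51 h | 49–53 | 52 | >52 to 53 |
| 54 h | 52–56 | 61 ECG, 63 PK | none |

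Neighbours overlap at 25–26, 28–29, 49–50 and 52–53 h, 1 h each. With 3 h spacing, intervals overlap once the tolerance exceeds 1.5 h, and readings cross the SAP cuts once it exceeds 1 h.

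**3. What a moved reading is.** If dose 2 is given at 24 h, a 24 h reading taken at 25–26 h is really 1–2 h post-dose. If dose 2 is at 25.5 h, the pre-dose ECG at 25.4 h goes to the 27 h cell and the true 3 h ECG at 28.5 h goes to the 30 h cell. The true 6 h ECG at 31.5 h also falls in the 30 h cell. Both are 1.5 h from 30 h, so the earlier is kept. The 24 h cell is empty, the 27 h cell holds a pre-dose value, the 30 h cell holds a 3 h value, and the real 6 h value leaves the by-visit summary.

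**4. Size, for the 24/27/30 h set.** The documents give no distribution of actual times. Assume each reading is even over its ±2 h.

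*Leaves its own window:* 1 h of 4 h = 25% at 24 h and at 27 h.

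*Independent readings, nearest-target rule:*
- 24 h cell empty: 0.25
- 27 h cell empty: 0.25 × 0.75 = 0.1875
- 27 h cell wrong: 0.25 × (0.25 + 0.25 × 0.5) = 0.094. The 27 h reading has either left, or lies at 25–26 h and is the farther of the two.
- 30 h cell wrong: 0.25 × 0.25 = 0.0625. The moved reading is 1–2 h from target, and the 30 h reading is farther with average probability 0.25.

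*Restricted to readings taken in sequence.* Each adjacent pair is out of order with probability 0.25 × 0.25 × 0.5 = 0.03125, so the sequence holds with probability 1 − 2 × 0.03125 = 0.9375:
- 24 h empty: (0.25 − 0.03125 − 0.25 × 0.03125)/0.9375 = 0.225
- 27 h empty: 0.75 × (0.25 − 0.03125)/0.9375 = 0.175
- 27 h wrong: 0.25 × (0.25 − 0.03125)/0.9375 = 0.058
- 30 h wrong: 0.03125/0.9375 = 0.033

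*All three shift by the same s, even on −2 to +2 h, as with a late dose:*
- 24 h empty and 27 h wrong: s > 1, 25%
- 30 h wrong: 3 − s ≤ s, so s ≥ 1.5, 12.5%

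The 48/51/54 h set has the same spacing and cuts, so the same fractions apply.

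**The case against.** Much of the case against a larger reading stands.

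- A reader might infer that the SAP routinely reports pre-dose readings as 3 h post-dose. It does not. That needs a repeat dose more than 1 h late, and Table 5-6 labels the cell 27 h from first dose, so 3 h post-dose is only its nominal meaning.
- A reader might take the 25% as the share of contaminated cells. It is the share leaving their own window. The nearest-target rule usually prefers the correct reading at 27 h, so empty cells are the main effect unless readings shift together.
- A reader might infer that a QT effect will look smaller. Mixing could do this, but the documents do not show it. QTc is also tabulated at the maximum post-baseline value, which relabelling cannot change. The most-extreme rule for notable values discards no extreme, and individual QTc actions use the actual readings.
- The aligned plots use time after dosing as the x-axis, and the SAP does not say whether that is windowed or actual time. Table 5-7 does not name PK, so applying its one-reading rule to PK is an inference. Pre-dose status of the 24 h and 48 h PK samples is also inferred.
- The 1-day arms are not exempt. Their 24 h reading also has ±2 h, and Table 5-6 is not cohort-specific, so a 25.5 h reading there would be filed at 27 h, a time those arms do not schedule.

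None of this removes the conflict: following both documents as written relabels compliant readings.

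**Conclusion.** The point holds as an inconsistency between the protocol tolerances and the SAP windows. It affects descriptive ECG and PK summaries by timepoint around the last dose in the 2-day and 3-day arms. The overlaps and crossings follow from the printed figures alone. The percentages rest on the assumed even spread: about 18–25% of 24 h and 27 h cells empty, 6–9% of 27 h cells and 3–6% of 30 h cells wrong, and 25% and 12.5% wrong under a common shift. Readings mostly within 1 h of target would make the effect negligible.

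The maximum-post-baseline QTc table, detection of notable values, non-compartmental parameters computed on actual times and the primary ACPR analysis are not affected. The documents do not support a conclusion about the direction of bias. The change is worth making because the SAP part is inexpensive, but it does not threaten the trial's main conclusions.

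**What to change.** **SAP 5.1.4 and Table 5-6.** For Day 2 and Day 3 ECG and PK, map each reading by actual time since the most recent dose. Label it pre-dose if it precedes that day's dose, and otherwise use 3 h and 6 h post-dose windows. In the example above, the ECGs at 25.4, 28.5 and 31.5 h become pre-dose, 3.0 h and 6.0 h. State which rule in Table 5-7 governs PK and whether the aligned plots use actual time.

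**Protocol Tables 6-2 to 6-4.** Reconcile the tolerances with the SAP windows so that no two nominal times share a permitted interval. Re-mapping alone does not settle this. With dose 2 on time, a compliant 27 h reading at 28.5 h is 4.5 h post-dose, midway between the 3 h and 6 h targets. The ±30 min already in the same note is one option; the documents do not require it.

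**Cost.** The SAP change is a small derivation using dose and assessment times already recorded, and it can be applied to data already collected. A tighter tolerance would slightly reduce scheduling flexibility on the ward, where patients remain until Day 4.
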